## Study Summary

Title	Neural response to food stimuli: fMRI changes following cognitive behavioral therapy for binge eating disorder
Short Title	NEURAL RESPONSE BED
IRB Number	829018
Phase	Phase 4
Methodology	Randomized, waitlist controlled, open label
Study Duration	3 years
Study Center(s)	Single-center
Objectives	The purpose of this research is to conduct a randomized controlled trial (RCT) assessing the impact of CBT on neural responses to binge eating stimuli. Females with a BMI $\geq$ 25 kg/m  and BED will be randomized to either a 16-week, one-on-one CBT intervention (n=20) or a waitlist control (WL; n=20). Both groups will have blood oxygen level-dependent (BOLD) functional magnetic resonance imaging (fMRI) scans at baseline and after the 16-week intervention. During the scans, participants will complete the following tasks: 1) food-specific stop signal task (SST), and 2) script-driven imagery of binge foods.
Number of Subjects	40
Main Inclusion and Exclusion Criteria	Key Inclusion: BMI $\geq$ 25 kg/m  ; binge eating disorder as diagnosed by DSM-5 criteria; female  Key Exclusion: Weight > 158.8 kg; left-handedness; pregnancy or lactation; current diagnosis of severe major depression or other psychiatric disorder that significantly interferes with daily living; active suicidal ideation; presence of conditions that may interfere with magnetic resonance imaging; use of weight loss medications or other agents known to affect body weight or blood glucose; type 1 or 2 diabetes mellitus; visual, auditory, or other impairment affecting task performance
Reference therapy	Waitlist control group
Statistical Methodology	Mixed-effects linear models
Safety Evaluations	Adverse events
Data and Safety Monitoring Plan	Drs. [name] and the co-investigators will be responsible for monitoring the data quality and the ongoing safety of subjects.

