## 3 Study Endpoints

### 3.1.1 Primary Study Endpoints

The primary endpoints are baseline to 16-week changes in BOLD fMRI response to food-specific SST and to binge-eating script-driven imagery.

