#### Imaging Procedures

**Pre-scan preparation.** Visits on imaging days will begin in the morning at the Hospital of the University of Pennsylvania. Upon arriving, participants will be greeted by research staff who will re-administer the MRI-eligibility checklist to ensure no changes have occurred that would render MRI unsafe or uncomfortable. The MRI technician will review this checklist. All participants will be asked about pregnancy status. For those who are unsure, a urine pregnancy will be completed prior to the scan. Those who attest to being pregnant or test positive will be withdrawn.

Participants will change into a hospital gown and be weighed, without shoes, on a calibrated electronic scale (BWB 800S, Tanita Corp., Tokyo, Japan) and will have their waist circumference and blood pressure measured. They will then complete a self-report measure of current mood (i.e., the Profile of Mood States, Brief Form^68) and visual analog scales for stress, hunger, food

[figure not shown]

Figure 1. Summary of Assessment Visit. POMS-BF=Profile of Mood States, Brief Form; VAS=Visual analog scales for stress, hunger, food cravings, fatigue; RSDI Scale=Response to Script-Driven Imagery Scale; BE=binge eating; EDE=Eating Disorder Examination; RBEDS=Reward-Based Eating Drive Scale; TFEQ=Three Factor Eating Questionnaire; BDI=Beck Depression Inventory

cravings, and fatigue level. They also will be required to demonstrate understanding of the task and use of the response device prior to entering the scanner.

**Imaging equipment.** We will use a clinically approved 3.0 Tesla Siemens Prisma scanner equipped with 64-channel head coil. BOLD fMRI sequences include automatic higher order shimming and both prospective and retrospective motion correction. Gradient performance allows 4 mm isotropic voxels at TR=2 sec and 3 mm isotropic voxels at TR=3 sec (3T). The system uses a transmit/receive head coil.

The research scanner is equipped with stimulus delivery and monitoring systems for fMRI research. This includes Sanyo SXGA 4200 lumens projectors with Sanyo Long Throw zoom lens for rear-view/rear projection onto Mylar screens. Video signals are carried into the magnet room using a Lightwave FiberLynx optical-fiber VGA connection. Both the projector and the FiberLynx units are housed in custom RF shield boxes with filtered power receptacles. Images are viewed through mirrors mounted on the head coils.

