Audio stimuli will be presented via air-conduction headphones and an Avotec audio system which is equipped with two different styles of head phones to accommodate variance in patient head size. Responses will be monitored using a color-coded keypad made of non-ferromagnetic components (FORP Current Design Inc., Philadelphia, PA) installed at the 3T system.

The MRI scan procedures have been designed to last 55 minutes. To ensure completion of all scans, each procedure will be timed and every effort will be made to keep as close to the designated schedule as possible. In respect of time and data quality, if necessary, scans will be skipped or re-run at the discretion of the research team.

**Protocol for structural MRI (5 minutes).** A magnetization-prepared, rapid acquisition gradient echo (MPRAGE) image will be acquired for anatomic overlays of functional data and spatial normalization using the following parameters: TI/TR/TE=1100/1810/3.51ms, flip=9°, matrix=256x192, FOV=240x180mm, slices=160, slice thickness=1mm.

**Protocol for BOLD fMRI (~10 minutes).** Resting and Task fMRI data will be acquired using a whole-brain, single-shot, multi-slice, gradient-echo EPI sequence with the following parameters: TR/TE = 3000/32 ms, flip = 90°, FOV = 192 × 192 mm, matrix = 64 × 64, 46 slices, slice thickness/gap = 3 mm/0 mm. The resulting nominal voxel size was 3.0 × 3.0 × 3.0 mm. EPI acquisitions include a 20 second dummy-scan period allowing the magnetic resonance signal to reach steady-state.

**fMRI Tasks.** We will use two tasks to assess the impact of CBT on neural activity to food-cue tasks. Our tasks have been selected to target relevant cognitive and neural models of BED. The timing of the stimulus presentation will be synchronized with trigger pulses from the magnet in order to ensure precise temporal integration of stimulus presentation and fMRI data acquisition. These tasks will be presented in a fixed order with the food-specific SST occurring first and the binge-eating script-driven imagery second.

**BOLD fMRI Task (Food-Specific SST; ~25 Minutes).** The SST is a measure of response inhibition, or the ability to inhibit a prepotent response. In this task, we will use an event-related design. Participants will be asked to perform the SST using a modified version with high and low calorie food images as we have used in a current ongoing trial. Neutral items will include office

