### 6.2.3 Allocation to Interventional Group

Subjects who meet eligibility criteria and complete their baseline assessment visit will be randomly assigned to the intervention or waitlist condition. We will use a permuted randomized block design that randomly mixes blocks of different sizes (2 to 6) to assign 40 eligible participants to CBT or waitlist conditions using a one-to-one allocation ratio. This randomization design was selected due to the need to create exactly the same group sizes with a small sample. A statistician will conduct the randomization using a computer-generated algorithm.

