#### Loss of Confidentiality Risk

Because information about participant's identity and voice recordings will be collected and stored for research purposes, there is a chance that the information could be viewed or heard by others not associated with the research team and therefore, there is a potential for loss of confidentiality. Participants will only be audio recorded with their express permission, though there is a risk of loss of privacy or breach of confidentiality that may occur from disclosure of private information while being recorded. The study team will work to uphold the privacy of the participants in several ways. Communications made among study staff regarding participants will use ID numbers only and never include names or other personal information. All participant data and recordings will be kept in locked files. In all data sets, we will use ID numbers only. A separate dataset linking names with ID numbers will be accessible only by the primary study investigators.

If unforeseen risks are seen, they will be reported to the Office of Research Integrity and Compliance.

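### In an open-label trial, the rule for skipping or repeating scans has no objective criterion and arm is not said to be withheld from those who process, check or analyse the images

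*Combined protocol and SAP*

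**What the plan says.** All references are to the combined protocol and SAP.

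- **Design.** The Study Summary gives the methodology as "Randomized, waitlist controlled, open label". No role is described as masked to arm.
- **Endpoint.** Section 3.1.1: "The primary endpoints are baseline to 16-week changes in BOLD fMRI response to food-specific SST and to binge-eating script-driven imagery".
- **Acquisition rule.** Section 6.2.1, Imaging Procedures, says that, where needed and on grounds of time and data quality, "scans will be skipped or re-run at the discretion of the research team". The sentence before it says that each procedure is timed so that all scans get done. No motion limit, task-response limit, time cut-off or log is given.
- **Motion.** The same section lists "both prospective and retrospective motion correction" as a feature of the sequences. No rule for excluding a scan because of motion is described.
- **Order of events.** Section 6.2.3: participants who are eligible and "complete their baseline assessment visit will be randomly assigned to the intervention or waitlist condition". Baseline scanning therefore comes before allocation.
- **Coding of data.** Section 19, Loss of Confidentiality Risk: "In all data sets, we will use ID numbers only", and "A separate dataset linking names with ID numbers will be accessible only by the primary study investigators".
- **Analysis.** Sections 8.2.2 and 8.3 specify the models, an intention-to-treat approach and further analyses of protocol-compliant participants. They give no rule for skipped, repeated or unusable scans.

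**The concern.** A BOLD value for a region of interest depends on a chain of choices: whether a run is completed, whether it is repeated, which run is used, whether it passes quality control, and how the regional value is extracted. If the people making these choices know the arm, the choices can depend on it without any intent.

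Participants and therapists cannot be masked to CBT versus waitlist. Image handling can be, so this is a part of the primary endpoint that the plan could protect and does not. With about 15 completers per arm, a handful of decisions can move a group mean noticeably.

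**Working it through.** **1. Where arm knowledge could enter.**

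| Step | Could it depend on arm? | Basis |
|---|---|---|
| Baseline acquisition | No | Randomization follows the baseline visit (6.2.3) |
| Week-16 acquisition: skip or re-run | Yes, if the staff deciding know the arm | Open label; discretion without criteria (6.2.1) |
| Processing, quality control and regional extraction, both visits | Yes, if arm labels are visible | No statement that they are withheld |

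Section 7 (Waitlist Control Group) has staff confirm at the week-16 visit that waitlist participants have not sought treatment, so some staff at that visit know the arm. The documents do not say whether these staff also make the scan decisions.

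The endpoint is week 16 minus baseline. An arm-dependent choice at week 16 enters the change directly, with no matching effect at baseline to cancel it.

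**2. How often the discretion might be used.** The allotted scan times are 5 + 10 + 25 + 15 = 55 minutes, which is the whole planned procedure; the visit plan allows 60 minutes in the scanner. The stated trial timings point in two directions:

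- Script imagery: 4 × (1 + 2.5 + 1) = 18 minutes, or 4 × (1 + 2.5 + 0.5 + 1) = 20 minutes if the silent 30 seconds are additional, against about 15 allotted.
- Stop-signal task: 4 blocks × 64 trials × 2.5 s = 640 s, about 10.7 minutes, against about 25 allotted.

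The first suggests pressure on the task that always runs second; the second suggests slack. The frequency of skips and re-runs cannot be settled from the documents.

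**3. The plan's own power figure.** Inputs: 40 enrolled and 25% dropout (6.1), so 40 × 0.75 = 30 completers, 15 per arm; effect 0.93, one-sided 5%, 80% power (8.1). A two-sample t test (noncentral t, 28 degrees of freedom) gives 79.9% power at 0.93 and a detectable effect of 0.931. The figure reproduces.

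**4. Sensitivity to an assumed bias.** Take the same test with no true effect and a spurious between-arm shift *b*, in SD of BOLD change, in the hypothesised direction. The false-positive probability is P(T > t₀.₉₅,₂₈), with T noncentral t and noncentrality *b*√(15/2).

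| Assumed shift *b* (SD) | One-sided error per region |
|---|---|
| 0 | 5.0% |
| 0.1 | 8.4% |
| 0.2 | 13.3% |
| 0.3 | 20.0% |

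To give these shifts a scale: if *k* of 15 change values in one arm are each replaced by values 1 SD higher, the arm mean moves by *k*/15, which is 0.07, 0.13 or 0.20 SD for *k* = 1, 2 or 3. If two values lying 1 SD below the arm mean are dropped instead, the denominator becomes 13 and the mean moves by 2/13 = 0.15 SD.

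**5. Loss of scans without bias.** Losing 1, 2 or 3 usable scans per arm cuts power at 0.93 from 79.9% to 77.4%, 74.5% or 71.3%.

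The shifts in step 4 and the losses in step 5 are assumptions. The documents give neither.

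**The case against.** The strongest reply is that the discretion is bounded. It is tied to time and data quality, applies only if necessary, and follows a sentence about completing every scan. The schedule leaves little room for repeats. Nothing says that scanner staff know the arm or see regional contrasts while scanning, so it is not shown how a re-run would push the result in a chosen direction. Intake, CBT, randomization and scanning involve different roles or places. Section 8.1 also sets the power calculation against exploratory neuroimaging standards.

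Much of this stands. The grounds are stated, scanner staff's knowledge of arm is an inference from the open-label design, and no directional mechanism is demonstrated. What remains is that grounds are not criteria, that nothing separates knowledge of arm from scan decisions, and that nothing withholds arm during processing or analysis.

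A reader might go further in three ways that the documents do not support:

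- *That ID-coded data would remove the bias at no cost.* ID-only data sets are already planned, and coding a file cannot undo a decision made at the scanner. The gap is that arm is not said to be withheld.
- *That motion exclusions are being made unmasked.* No motion-exclusion step is described. It can only be said that, if one is applied, it is neither specified nor masked.
- *That a particular share of the target effect is at risk.* Any such share depends on assumed numbers of runs and assumed shifts.

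**Conclusion.** The point holds as a low-cost improvement, not as a demonstrated bias. The acquisition rule has no objective criterion, and arm is not said to be withheld from anyone who processes, checks or analyses the images. Baseline acquisition is protected by the timing of randomization.

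The size of any bias is unknown. The error rates of about 8% to 20% are a sensitivity range for shifts of 0.1 to 0.3 SD, assuming 15 completers per arm, a simple two-sample comparison of change, and a shift in the favoured direction. The planned sample size and power calculation are unaffected.

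**What to change.** 1. State that preprocessing, quality exclusion and region-of-interest extraction, for both visits, are done on the ID-coded files with arm labels withheld. Merge the allocation file only after the regional values are locked.
2. Replace the discretion sentence with pre-set triggers for skipping or re-running a scan, for example session time reached or a fixed motion or task-response limit. Log each use with its reason.
3. Report skipped, re-run and excluded scans by arm.

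The first change addresses processing and quality control; the second and third address decisions at the scanner, which coding cannot reach. Together they reduce the risk of bias but do not remove it.

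The cost is procedure wording, a simple log, later merging of one file and slightly less flexibility at the scanner. No extra staff, scans or participants are needed.

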### 6.2.2 Post-Treatment Visit (Waitlist Group Only)

After individuals in the WL group complete their second fMRI assessment, they will be offered CBT treatment. For Specific Aim 3, the WL group will be asked to complete a brief assessment after their last CBT session to measure treatment response (i.e., the number of BE episodes in the past 28 days).

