### 2.1 Primary Objective

**Aim 1:** Compare differences between the CBT and WL groups at week 16 in changes in BOLD fMRI response to the food-specific SST.

Hypothesis 1: Since CBT for BED involves successful management of dietary disinhibition, we propose that participants will have favorable pre- to post-treatment changes in regions of interest (ROIs) that are associated with inhibitory control. We hypothesize that the CBT group, compared with the WL group, will have increased activation in the PFC, IFG, OFC, and insula during the food-specific SST.

**Aim 2:** Compare differences between the CBT and WL groups at week 16 in changes in BOLD fMRI response to recall of binge foods (i.e., script-driven imagery).

Hypothesis 2: CBT teaches participants how to reduce responsiveness to binge foods. Thus, we propose that CBT will alter neural responses in regions that promote food reward. We hypothesize that after treatment, the CBT group, compared to the WL group, will have decreased activation in the PFC, OFC, insula, VTA, and VS in response to script-driven imagery of binge foods.

**Aim 3:** Determine whether pre-treatment neural activation on the SST and script-driven imagery task predict differences between CBT responders and non-responders ( $\geq 1$  binge eating episode in the past 28 days).

Hypothesis 3: Results from other psychiatric disorders show that patients with greater dysfunction in neural circuitry related to their disease are less likely to respond to treatment. We predict that relative to CBT responders, non-responders will have lower pre-treatment BOLD activation in the inhibitory control ROIs during the SST and higher pre-treatment BOLD activation in the reward ROIs during the script-driven imagery task.

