4: Final stage	Provide education about realistic expectations Devise a short-term plan for the months following treatment Devise a long-term plan to minimize relapse in the future	15-16

**Waitlist Control Group.** Participants who are assigned to the wait-list group will complete their assessment visits at baseline and 16 weeks. We will request that they not seek treatment for weight or binge eating disorder during the wait period. This will be verified at a brief telephone call check-in at week 8 where we will also update the patient on their study status, as well as at the week 16 visit. After they complete their post-treatment assessment, they will be offered the 16-week cognitive behavioral therapy treatment. At their last treatment session, they will be asked to complete a brief assessment on the effect of the CBT treatment.

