### 7.1 Vulnerable Populations:

Children, pregnant women, fetuses, neonates, or prisoners are not included in this research study. Although not directly targeted, mentally disabled persons, economically or educationally disadvantaged persons, and/or employees or students of the University of Pennsylvania will not be denied enrollment and any special protections and/or additional safeguards will be undertaken in order to protect the rights and welfare of these subjects from coercion or undue influence as appropriate.

Table 2. Study Assessment Schedule

	Waitlist Group Only					
	Screen	T1	Intervention or Waitlist (16 weeks)	T2	Intervention (16 weeks)	T3
Informed Consent- General	X					
Informed Consent- Audiorecording BED Assessment	X			X		X
Informed Consent- Audiorecording treatment sessions	X		X		X	
Demographic and Clinical Variables						
Review inclusion/exclusion criteria	X					
Demographics	X					
Medical history and physical exam	X					
Prior/concomitant medications	X			X		X
Review medication changes and updates				X		X
Vital signs (BP, HR)	X					
Pregnancy test	X					
MINI	X					
Menstrual diary	X	X	X	X		
BMI	X	X	X	X		X
Profile of Mood States (Brief Form)		X		X		
Scales for stress, hunger, food cravings, fatigue		X		X		
Responses to Script-Driven Imagery Scale		X		X		
Outcome Measures						
fMRI scan (SST, Script-driven imagery)		X		X		
Eating Disorder Examination	X			X		X
Reward-Based Eating Drive Scale		X		X		
Three Factor Eating Questionnaire		X		X		
Additional Questionnaires (described in Section 6.2)		X		X		X
Intervention adherence/fidelity						
Sessions attended, skill builders completed			X			
Adverse event/unanticipated problems assessment		X	X	X		X

Note. T1=Baseline; T2=16 week follow-up. T3=Assessment of post-CBT treatment outcomes for the waitlist group only. SST=Stop signal task.

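### Aim 3 sets no condition on binge status when delayed CBT starts, so a waitlist woman abstinent both before and after CBT is labelled a CBT responder

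*Combined protocol and SAP*

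**What the plan says.** Section 2.1 sets Aim 3: "Determine whether pre-treatment neural activation on the SST and script-driven imagery task predict differences between CBT responders and non-responders". A non-responder has at least one "binge eating episode in the past 28 days", so a responder has none. This is an end-state rule that does not refer to where the woman stood when treatment began.

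Section 6.2.2 gives the timing for the WL arm: "For Specific Aim 3, the WL group will be asked to complete a brief assessment after their last CBT session to measure treatment response". The measure is given as "i.e., the number of BE episodes in the past 28 days", with no further criterion. The Table 2 note agrees: "T3=Assessment of post-CBT treatment outcomes for the waitlist group only".

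Entry to delayed CBT depends only on finishing the week-16 assessment. Section 6.2.2: "After individuals in the WL group complete their second fMRI assessment, they will be offered CBT treatment". Section 7 and the waitlist paragraph under Potential Study Risks (Section 19) say much the same. The weekly-for-3-months binge criterion is an inclusion criterion (Section 5.2), and Table 2 reviews eligibility at Screen only. Section 5.4 puts a WL woman on the waitlist for about 5 months.

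Table 2 marks the Eating Disorder Examination (EDE) at Screen, T2 and T3. Binge status at the end of the wait will therefore be on file, but no section links it to Aim 3. Section 8.2.2 gives no Aim 3 model, and its only responder analysis is a between-group chi-square test.

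**The concern.** A remission recorded at T2, before the first CBT session, can be credited to CBT at T3. The plan already leaves room for such women. Its chi-square test compares responder percentages between groups, and at week 16 the WL arm is untreated. The same woman can count there as a responder without CBT and in Aim 3 as a responder to CBT.

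Hypothesis 3 is about who responds to treatment, and the Background presents the work as a basis for neural markers of CBT outcome. Women who remitted untreated mix prognosis with treatment response. If milder neural dysfunction also favours untreated remission, the contrast is pushed towards the hypothesis; if not, it is diluted. With about 30 completers, a few labels matter.

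**Working it through.** **Inputs from the documents**
- 40 randomised 1:1 (Sections 5.1, 6.2.3); 25% drop-out leaves 30 completers (Section 6.1), taken as 15 per arm.
- 50% full remission expected with CBT (Section 7).
- Detectable effect 0.93, 80% power, one-sided 5% (Section 8.1).

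**Assumptions**
- The documents give no untreated remission rate. I take r = 5%, 10%, 20% or 30% of WL completers abstinent at T2.
- For the upper bound, all of them take up CBT, reach T3 and stay abstinent.
- The two arms are pooled for Aim 3. Section 6.2.2 implies this but does not say so.

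**Step 1: the plan's own figure.** Two-sample t-test, 15 per group, noncentral t with 28 df and noncentrality 0.93 × √(15 × 15/30) = 2.55. Power is 79.95% and the detectable effect is 0.931, so 0.93 reproduces on 15 completers per arm. It was stated for BOLD signal between groups. I carry it to Aim 3 only as an illustration, because 50% remission among 30 women also gives 15 against 15.

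**Step 2: how many labels are affected (upper bound).** Affected women m = 15r. Pooled responders R = 7.5 (CBT arm) + m + 0.5 × (15 − m). WL responders = m + 0.5 × (15 − m).

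| r | m | R | m/R | m/WL responders |
|---|---|---|---|---|
| 5% | 0.75 | 15.375 | 4.9% | 9.5% |
| 10% | 1.5 | 15.75 | 9.5% | 18.2% |
| 20% | 3.0 | 16.5 | 18.2% | 33.3% |
| 30% | 4.5 | 17.25 | 26.1% | 46.2% |

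**Step 3: with relapse.** If only half of the T2-abstinent women are still abstinent at T3 (an assumption), the relapsers become non-responders. Then R = 7.5 + 0.5m + 0.5 × (15 − m) = 15, and the share is 0.5m/15 = 2.5%, 5%, 10%, 15%.

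**Step 4: cost of excluding T2-abstinent WL women.** Each response group has (30 − m)/2 women.

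| r | n per response group | Detectable effect |
|---|---|---|
| 5% | 14.625 | 0.943 |
| 10% | 14.25 | 0.956 |
| 20% | 13.5 | 0.984 |
| 30% | 12.75 | 1.014 |

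**Step 5: power with and without the rule.** Suppose half of the m women have the activation of non-responders. A true effect of 0.93 then shrinks to 0.93 × (1 − 0.5m/R) = 0.907, 0.886, 0.845, 0.809. Power is about 78%, 76%, 73%, 69% as the plan is written, against 79%, 78%, 76%, 74% with these women excluded.

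**Step 6: could the WL arm at T2 serve as an untreated comparator?** With 1, 2, 3 or 4 abstinent among 15, the detectable effect (same test, 80% power, one-sided 5%) is about 2.7, 2.0, 1.7 or 1.5 SD.

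**The case against.** The strongest reply is that the problem is small and the remedy only partial.

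- **Size.** The Background calls BED chronic, which points to the low end of the range without giving a rate. Step 2 is a ceiling: it assumes full uptake and persistence, and it allows no loss between T2 and T3. At the plan's 50% remission rate, half of the affected women might have responded to CBT anyway. This stands.
- **Gain in power.** Step 5 shows about one percentage point at the low end and five at the high end. This stands. The case for the rule rests on what the label means, not on power.
- **Untreated remission in the CBT arm.** Some immediate-CBT women would also have remitted untreated, and no rule can find them. Restricting only the WL arm also selects women whose bingeing lasted through the wait. This stands as a limit, but the WL case differs because the remission is observed and dated before CBT.
- **Which scan.** The plan does not say whether the WL pre-treatment scan is T1 or T2. A T1 scan predicts across an untreated 16-week wait; for a woman who remitted, a T2 scan comes after remission. The labelling problem exists either way, but the rule is incomplete until this is settled.

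A reader might infer that every woman who stops bingeing during the wait becomes a CBT responder. The documents do not support that: she must accept an offered treatment, be assessed at T3 and have no episode in the last 28 days. If she relapses, she is a non-responder.

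**Conclusion.** The point holds as a defect in a stated classification rule. Followed as written, the plan labels a WL woman abstinent at both T2 and T3 a CBT responder, although the T2 record shows abstinence before CBT began. The size cannot be fixed from the documents. Under assumed T2 abstinence of 5% to 30% the ceiling is about 0.8 to 4.5 of 15 women, or 5% to 26% of pooled responders; with half relapsing it is 2.5% to 15%.

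Two stronger readings are not supported. The primary endpoints (Section 3.1.1) are changes in BOLD response, and Aims 1 and 2 do not use this rule, so the trial's main comparison is untouched. Nor would correcting the rule make Aim 3 a test of response caused by CBT, since untreated remission inside the CBT arm remains.

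**What to change.** Amend the Aim 3 text and add an Aim 3 paragraph to Section 8.2.2, before outcome data are examined:

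1. Include a WL participant in the main Aim 3 analysis only if her T2 EDE shows at least one binge episode in the prior 28 days.
2. Report the version with all WL participants as a sensitivity analysis.
3. State whether the WL pre-treatment scan is T1 or T2.
4. Word conclusions as prediction of outcome after CBT.
5. Keep any look at whether activation predicts T2 abstinence in the WL arm descriptive. With 1 to 4 events in 15 women (Step 6), it cannot serve as a rule for calling a marker prognostic.

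No new data are needed and who is offered CBT does not change. The cost is the loss of the few T2-abstinent WL women from the main Aim 3 analysis, with the detectable effect rising from 0.93 to about 0.94 to 1.01 over the assumed range.
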